#### 2.3.3. Faecal sampling and DNA isolation

Faecal samples were collected one day before the start and at the end of the intervention. The samples were frozen immediately and stored at -20 °C until use. DNA was isolated within one week after sampling. DNA isolation was performed in parallel using the protocol for isolation of DNA from faecal samples described by Yu and Morrison (2004) [9].

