### 1.1. Objective

The purpose of this study was to investigate if daily consumption of barley beta-glucans effect lipid and glucose metabolism and alter intestinal microbiota composition in participants with metabolic syndrome or with high risk for metabolic syndrome development. We conducted 4-week long, placebo controlled dietary study, where participants consumed bread with (test group) or without (control group) enriched beta-glucans bread.

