#### 2.3.4. Microbial community analysis

**DGGE:** PCR-DGGE fingerprinting was performed to check the quality of isolated DNA between parallel samples and to compare the individual profiles. PCR-DGGE analysis was performed as described by Matijašić et al. (2014) [10].

**Real-time PCR analysis** was performed by an established procedure for quantification of bacteria in faecal samples [10] with slight modifications using a ViiA™ 7 Real Time PCR System (Applied Biosystems, USA). Data were analysed with ViiA™ 7 Software 1.2.2 (Applied Biosystems, USA).

**Next generation pair end sequencing:** For 16S rRNA sequencing, 23 participants were chosen randomly among those with both samples qualified for sequencing after DGGE examination. In total, 46 samples from 14 persons in the test group and nine persons in the control group were examined.

The Illumina Miseq platform with v.3 2x300 pair end technology was used for sequencing V3 and V4 16S rRNA regions (Microsynth). After demultiplexing, raw reads were processed following the UPARSE pipeline (Usearch v.8, June 2015) [11]. Stringent quality filtering based on a low expected number of errors was used for OTU formation with algorithm parameters optimized after mock sample analysis (34 strains). With relaxed quality filtered sequences, more than 91 % of raw reads could be placed into an OTU with a 0.03 distance criterion. Presumptive OTU identity was determined with the 'usearch\_global' function searched against Silva NR SSU v.119 and LTP SSU type strains v.121 database. Taxonomy was assigned to OTUs with Wang et al.'s (2007) [12] method implemented in Mothur v.1.35 and the RDP training set 14 [13]. FastTree2 was used for the generation of an approximately maximum-likelihood phylogenetic tree [14]. Taxonomy, the OTU table and the phylogenetic tree were handled with the 'R' package Phyloseq for statistical analysis and graphics [15].

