## 3. STATISTICS

For analysis of participants' anthropometric and metabolic characteristics, RT-PCR results and microbial richness and diversity measures, a Wilcoxon signed-rank test or paired samples *t*-test were used as appropriate with  $P < 0.05$  for significance and  $P < 0.1$  for reporting a trend (SPSS v.21). Statistical sequence analysis was based on differential abundance testing using the 'R' package DESeq 2 [16]. Differential abundance that occurred in test group subjects after dietary intervention but not in the control group was determined in a model with interaction (time, group and subject). Significance was reported for  $P < 0.05$  after multiple inference correction (Benjamini-Hochberg), and all OTUs with  $P < 0.05$  before correction were screened for trends. Initial microbial abundance differences between test group subjects who responded to dietary intervention with a 10 % plasma total cholesterol concentration drop and those without reduction were also tested with Deseq2 [16]. OTUs with  $P < 0.1$  after correction were considered significant. Alpha and beta diversity measures and PCoA of weighted UniFrac distances were calculated and plotted with Phyloseq [15].

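### The paired RT-PCR, richness and diversity tests cannot separate change over time from a shift between DNA extractions made at least three weeks apart

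*SAP*

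**What the plan says.** On timing, SAP section 2.3.3 says "Faecal samples were collected one day before the start and at the end of the intervention" and that "DNA was isolated within one week after sampling". SAP section 1.1 gives the interval: "We conducted 4-week long, placebo controlled dietary study".

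On checks of the extraction, section 2.3.3 adds "DNA isolation was performed in parallel using the protocol for isolation of DNA from faecal samples", and section 2.3.4 says "PCR-DGGE fingerprinting was performed to check the quality of isolated DNA between parallel samples and to compare the individual profiles". Read together, these most naturally mean replicate isolations of the same sample. Neither document describes extraction sessions, reagent lots, extraction controls or how samples were allotted to sessions.

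On analysis, SAP section 3 says that for anthropometric and metabolic characteristics and for "RT-PCR results and microbial richness and diversity measures, a Wilcoxon signed-rank test or paired samples" *t*-test was chosen as appropriate, at P < 0.05 with P < 0.1 reported as a trend. It gives no between-arm comparison and no session term for RT-PCR, richness or diversity. OTU abundance is handled differently, with a DESeq2 model that includes an interaction of time, group and subject.

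**The concern.** DNA extraction is a step at which yield and composition can shift with reagent lot, operator or day. If a participant's two samples are extracted together, such a shift drops out of the paired difference. Here they cannot be extracted together, so within one person the visit and the extraction session are the same contrast.

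A paired test within one arm has nothing to subtract the shift from. If many participants share it, it is read as an effect of four weeks of bread on bacterial numbers or diversity. Microbiota composition is the first hypothesis in SAP section 1.2, so a false signal here would bear on a main claim of the trial. The control arm was processed under the same one-week rule and could remove the shift, but section 3 does not use it for these outcomes.

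**Working it through.** The documents contain no power, sample-size or session-effect figure to reproduce. The one related count agrees: 2 × (14 + 9) = 46 sequenced samples (SAP section 2.3.4).

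**Step 1. Timing.** Call the day before the first bread day 0 and the end of the intervention day 28.
- Latest extraction of the first sample: 0 + 7 = day 7.
- Earliest extraction of the second sample: day 28.
- Minimum gap: 28 − 7 = 21 days. Maximum gap: (28 + 7) − 0 = 35 days.

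**Step 2. What each test estimates.** For participant *i*, observed change = true change + (after-session effect − before-session effect) + noise.
- The within-arm paired test estimates true change plus the mean session difference.
- Test minus control estimates the difference in true change plus the difference between arms in mean session difference. The last term is zero for a shift common to both arms.

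**Step 3. A shift shared by all participants, with no true change.** Inputs: two-sided 5% level (assumed, as sidedness is not stated); n = 14 and n = 9, the sequenced participants by arm; shift δ in SDs of the within-person change (assumed range 0 to 1). Rejection rate = P(|T| > t₀.₉₇₅,ₙ₋₁), where T is noncentral t with n − 1 degrees of freedom and noncentrality δ√n. For example, δ = 0.5 and n = 14 gives 0.5 × 3.742 = 1.871, and a rejection rate of 41%. The last two columns come from simulation with 40,000 runs.

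| Shift δ | Test arm, n = 14 | Control arm, n = 9 | P < 0.05 in test arm but not in control | Between-arm t-test of change |
|---|---|---|---|---|
| 0 | 5% | 5% | 5% | 5% |
| 0.25 | 14% | 10% | 13% | 5% |
| 0.5 | 41% | 26% | 31% | 5% |
| 0.75 | 74% | 51% | 36% | 5% |
| 1 | 93% | 75% | 24% | 5% |

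If the SD of change were 0.4 log10 copies (assumed), the shifts of 0.25, 0.5 and 0.75 SD would be 0.1, 0.2 and 0.3 log10. At the P < 0.1 trend level, the test arm is flagged in 23% of runs at 0.25 SD and in 55% at 0.5 SD. The between-arm t-test is a simple stand-in for the DESeq2 interaction, not a replica of it.

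**Step 4. How much depends on enrolment.** Let each session have its own random effect with SD 0.15 log10 (assumed), the SD of change be 0.4, and 14 pairs be processed in waves that share a before session and an after session. Simulated false-positive rates of the paired t-test are 35% with one wave, 20% with two, 15% with three, 10% with five, and 5% when all 14 pairs have sessions of their own. In that last case the cost is noise only. The variance of the paired difference is multiplied by (0.16 + 2s²)/0.16, which is 1.13, 1.28 and 1.50 for session SD s = 0.10, 0.15 and 0.20.

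**Step 5. Limit of the between-arm comparison.** If a shift fell on the test arm alone, the between-arm test would reject in 8.5%, 20% and 61% of runs at 0.25, 0.5 and 1 SD. Balance of sessions over arms therefore has to be shown.

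**The case against.** The strongest reply is that nothing in the documents shows that a shift occurred, or that sessions lined up with visit across participants. Recruitment ran through community health centres and family doctors (SAP section 2.1), which could mean staggered entry and mere noise. This stands: bias depends on enrolment and session dates that are not given. It does not dispose of the point, because step 4 shows that even five shared waves double the error rate under the stated assumptions.

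The sample sizes are also open to challenge. The 14 and 9 are the sequencing subset; section 2.3.4 does not limit RT-PCR to them and gives no RT-PCR count. The RT-PCR procedure is delegated to a cited paper, so whether counts were normalised for DNA yield cannot be seen. Both objections stand, and the rates are illustrations only.

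The DGGE step had a second purpose, comparing individual profiles, and both samples had to qualify before sequencing. That is some quality control, but it does not show equal yield across sessions weeks apart.

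Two stronger readings are tempting. A reader might infer that the OTU results are confounded too. The documents do not support that: the control arm followed the same rule, a common shift cancels in the time-by-group interaction, and randomisation with blinding makes sessions that follow arm less likely. A reader might also infer that the one-week rule is itself the flaw. It keeps frozen storage short and similar for both samples. Extracting both in one session would store every first sample about four weeks longer than its partner, so storage time would follow visit in everyone.

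Finally, it can be said that this is mostly the familiar weakness of within-arm testing. The remedy is indeed the same; the extraction schedule is a specific reason why it matters for these outcomes.

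**Conclusion.** The point holds for RT-PCR, richness and diversity. That a participant's two extractions are at least about 21 days apart follows from the SAP's own timing. That the paired tests cannot separate session from time follows from section 3. Whether this produced bias is unknown.

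If a shift was shared by many participants, the false-positive rate rises above 5%: 14% at 0.25 SD and 41% at 0.5 SD with 14 pairs, 10% and 26% with 9. If sessions were fully staggered, the rate stays at about 5% and only precision suffers. These figures rest on an assumed shift, a t-test on normally distributed changes and the sequencing counts; none is a stated property of the RT-PCR data. They apply most directly to a yield-dependent outcome, and no separate calculation was made for richness or diversity. The DESeq2 interaction is not affected by a shift common to both arms.

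**What to change.** In SAP section 3, replace the within-arm paired tests for RT-PCR, richness and diversity with a between-arm comparison of change (test minus control), for example a regression of the after value on arm and the before value. State that the within-arm changes are descriptive. Report extraction dates or sessions, and reagent lots if recorded, by arm and visit, so that readers can judge whether the arms were balanced over sessions.

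This needs no new samples and can be done although the SAP was written after the trial was completed. The cost is precision. With equal SDs of change and the sequencing counts, the standard error relative to the test arm's own paired mean is √[(1/14 + 1/9)/(1/14)] = √(0.1825/0.0714) = 1.60 times as large, before any gain from baseline adjustment.

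Do not require a change to the one-week rule. Re-extraction of both samples in one session is at most an optional sensitivity check, if stool was retained; the documents do not say that it was.

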#### 2.3.4. Microbial community analysis

**DGGE:** PCR-DGGE fingerprinting was performed to check the quality of isolated DNA between parallel samples and to compare the individual profiles. PCR-DGGE analysis was performed as described by Matijašić et al. (2014) [10].

**Real-time PCR analysis** was performed by an established procedure for quantification of bacteria in faecal samples [10] with slight modifications using a ViiA™ 7 Real Time PCR System (Applied Biosystems, USA). Data were analysed with ViiA™ 7 Software 1.2.2 (Applied Biosystems, USA).

**Next generation pair end sequencing:** For 16S rRNA sequencing, 23 participants were chosen randomly among those with both samples qualified for sequencing after DGGE examination. In total, 46 samples from 14 persons in the test group and nine persons in the control group were examined.

The Illumina Miseq platform with v.3 2x300 pair end technology was used for sequencing V3 and V4 16S rRNA regions (Microsynth). After demultiplexing, raw reads were processed following the UPARSE pipeline (Usearch v.8, June 2015) [11]. Stringent quality filtering based on a low expected number of errors was used for OTU formation with algorithm parameters optimized after mock sample analysis (34 strains). With relaxed quality filtered sequences, more than 91 % of raw reads could be placed into an OTU with a 0.03 distance criterion. Presumptive OTU identity was determined with the 'usearch\_global' function searched against Silva NR SSU v.119 and LTP SSU type strains v.121 database. Taxonomy was assigned to OTUs with Wang et al.'s (2007) [12] method implemented in Mothur v.1.35 and the RDP training set 14 [13]. FastTree2 was used for the generation of an approximately maximum-likelihood phylogenetic tree [14]. Taxonomy, the OTU table and the phylogenetic tree were handled with the 'R' package Phyloseq for statistical analysis and graphics [15].

## 2.4. Secondary outcome measures

After 4 weeks of dietary intervention protocol of primary outcome measures was repeated.

## 2.5. Missing data

Due to complex presentation of data for changes in gut microbiota composition, we can't provide results for primary and secondary outcome measure of microbiota composition.

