## 1. INTRODUCTION

This document is established to provide information about dietary clinical trial "Impact of Consumption of Beta-glucans on the Intestinal Microbiota and Glucose and Lipid Metabolism". Document was prepared when clinical trial was completed and contains basic information about study design, protocol and methodology used.

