### 1.2. Hypothesis

1. 4- week consumption of beta-glucans alters the composition of intestinal microbiota and changes the ratio of different bacteria groups and consequently effects production of short chain fatty acids in a population with metabolic syndrome or with high risk for metabolic syndrome development.
2. 4- week consumption of beta-glucans has an influence on glucose metabolism and consequently improves insulin resistance within people with metabolic syndrome or with high risk for metabolic syndrome development.
3. 4 - week consumption of beta-glucans improves specific plasma lipid content in a population with metabolic syndrome or with high risk for metabolic syndrome development.

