**Figure 1: Participants flow diagram.**

## 2.2. Dietary intervention

Participants consumed bread with beta-glucans content of approximately 3,4 g beta-glucans per 100 g of bread in 4-week long intervention. Before study participants had two-week washout period without consuming any pre- and pro-biotics. Participants retained their usual eating habits during the

intervention. A 72-hour dietary recall was performed in order to control participants' diet and eating habits. Participants were told to consume 200 g of bread daily, not knowing whether the bread was experimental or control. Participants included in the test group consumed 200 g of BGB, containing more than 6 g of barley beta glucans, daily. Participants in the control group consumed 200 g of CWB without added beta glucans. 72-hour dietary recall was performed before intervention and at the end of the trial to evaluate daily nutrient and energetic input of each participant.

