### 2.3. Primary outcome measures

Participants gave blood and stool samples a day before intervention with barley beta-glucans. Blood sampling was performed for insulin resistance determination and for lipid profile determination (Total cholesterol, HDL-cholesterol, LDL-cholesterol, triglycerides). They also had option to give a blood sample for genetic investigation of genes associated with lipid metabolism (apoE).

Analysis were performed in accordance with health community centres in Ajdovščina and Ljubljana, Slovenia. Venous blood samples were obtained by professional medicine personnel for analysis of fasting glucose, lipids and insulin.

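### SAP section 2.5 says microbiota results cannot be given and does not say where they are; RT-PCR, richness and diversity get only within-group tests, and short-chain fatty acids get no analysis

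*SAP*

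**What the plan says.** SAP section 2.5 (Missing data) is a single sentence. It opens "Due to complex presentation of data for changes in gut microbiota composition" and concludes that "we can't provide results for primary and secondary outcome measure of microbiota composition". It says nothing about lost samples, reasons for loss, the analysis set or how gaps are handled.

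Microbiota is a primary outcome by the SAP's own layout. Section 2.3 (Primary outcome measures) begins "Participants gave blood and stool samples a day before intervention with barley beta-glucans", section 2.3.4 sets out the microbial analysis, and section 2.4 makes the 4-week repeat of the same measures the secondary outcome. Hypothesis 1 in section 1.2 is that beta-glucan consumption "alters the composition of intestinal microbiota and changes the ratio of different bacteria groups and consequently effects production of short chain fatty acids".

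On laboratory work, section 2.3.4 says that real-time PCR "was performed by an established procedure for quantification of bacteria in faecal samples", and that for sequencing "23 participants were chosen randomly among those with both samples qualified for sequencing after DGGE examination": 14 in the test group and nine in the control group, 46 samples in all.

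On analysis, section 3 gives:
- paired t-tests or Wilcoxon signed-rank tests for RT-PCR, richness and diversity;
- a DESeq2 model with a time, group and subject interaction for OTUs, with Benjamini-Hochberg correction;
- a second DESeq2 comparison, within the test group, of initial abundance in cholesterol responders and non-responders;
- alpha and beta diversity and weighted UniFrac ordination, calculated and plotted.

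It adds, in the past tense, that significance was reported after correction.

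Protocol section B.3 plans faecal butyric, acetic and propionic acid before and after the intervention.

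**The concern.** A primary outcome is said to have no results that can be provided, for a reason of presentation rather than of data. Counts, means, differences, intervals and a list of OTUs passing a corrected threshold all fit in tables. The SAP was written late ("Document was prepared when clinical trial was completed and contains basic information about study design, protocol and methodology used"), so it cannot serve as an advance record of what would be reported. It also gives no pointer to where the microbiota results are.

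Two further gaps affect the same hypothesis. For RT-PCR, richness and diversity, the only tests named compare each arm with its own baseline. For short-chain fatty acids, the SAP describes no analysis at all. Followed as written, the plan yields for Hypothesis 1 no microbiota result that it commits to report, no between-arm estimate for several of the measures, and no test of the fatty-acid part.

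**Working it through.** **1. Section 2.5 against section 3.** Section 2.5 says results cannot be provided. Section 3 describes completed analyses whose outputs are reportable. Both can be true, if the analysis was done and the results are simply not in this document, so this is not a contradiction. What is missing is an adequate reason or a location.

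**2. Sequencing counts (section 2.3.4).** 14 + 9 = 23 people, and 23 × 2 visits = 46 samples. The figures agree, so paired data exist for the sequenced subset.

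**3. What the paired tests estimate.** Write the expected change in the control arm as c and in the test arm as c + δ, where δ is the effect of beta-glucans.
- The paired test in the test arm examines c + δ = 0.
- The paired test in the control arm examines c = 0.
- The between-arm difference is (c + δ) − c = δ.

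Only the last isolates the randomised effect. A non-zero c is plausible here: SAP section 2.2 has both arms eat 200 g of bread daily and follows a two-week period without pre- or probiotics. The DESeq2 OTU analysis already has a group-by-time interaction, so this gap is confined to RT-PCR, richness and diversity.

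**4. Short-chain fatty acids.** Protocol section B.3: 3 acids, two time points. SAP section 1.2: named in Hypothesis 1. SAP sections 2.3, 2.4 and 3: 0 mentions of an outcome, assay or test.

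**5. Precision of the proposed between-arm estimate for the sequencing indices.** Inputs: n = 14 and 9 (section 2.3.4); a linear model with intercept, arm and baseline; similar baseline means assumed.
- SE = √(1/14 + 1/9) = √0.1825 = 0.427 residual SD
- df = 23 − 3 = 20, so t(0.975) = 2.086
- 95% half-width = 2.086 × 0.427 = 0.891 residual SD

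The number of people with RT-PCR data is not stated in the text available, so the same figure cannot be given for RT-PCR.

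**The case against.** The case on the other side has weight.

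- **The document describes itself as basic information on design and methods.** It contains no lipid or glucose tolerance results either, so the absence of microbiota results from it is not special. This stands, but only microbiota is singled out by a sentence saying its results cannot be provided.
- **Section 3 says significance was reported.** That points to reporting somewhere. A reader might infer from section 2.5 that the microbiota results were suppressed, or never reported; the documents do not support that. The SAP says they cannot be provided, without saying in what setting.
- **The list of RT-PCR groups may be in the cited procedure, and losses may be in the flow diagram** ("Figure 1: Participants flow diagram"), which is not shown. Both are fair. The unnamed groups and indices, and the lack of a missing-sample account, are therefore missing detail at most.
- **The metabolic characteristics tested in section 3 might be meant to include faecal fatty acids.** This is a stretch: they are not named, and section 2.3 has no measurement of them. Nor do the documents show whether they were measured, so it would also be wrong to conclude that they were not.
- **The SAP does not say that conclusions on richness or diversity rest on significance in one arm and not the other.** Correct. That contrast is described only for OTUs, in the interaction model. So no false conclusion is shown; the point is that no between-arm estimate is planned for the other measures.

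**Conclusion.** The point holds in a limited form. Section 2.5 contains no missing-data content, gives a weak reason for not providing results on a primary outcome, and does not say where they are. RT-PCR, richness and diversity have only within-group tests, which do not estimate the randomised comparison. The fatty-acid part of Hypothesis 1 has no outcome, assay or test in the SAP.

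Its size is a matter of scope rather than of error rate: one of three hypotheses, in both its parts; 46 sequenced samples from 23 people; three fatty acids planned in the protocol and none analysed in the SAP. No power or error figure is needed to establish it.

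It rests on reading section 2.3 and its subsections as the list of primary outcomes, which section 2.5's own wording supports. It does not depend on results being absent from other publications, which these documents cannot show. The change should be made, but nothing here shows that a reported conclusion is wrong.

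**What to change.** 1. Replace the sentence in section 2.5, by a dated note that keeps the present wording visible, with a commitment to report the microbiota outcome or a statement of where it is reported. Cover, whatever the P value: every RT-PCR group and every richness and alpha-diversity index analysed; beta diversity (weighted UniFrac); the DESeq2 interaction, with the number of OTUs tested and those passing Benjamini-Hochberg; and the DESeq2 responder comparison.
2. For RT-PCR groups and richness and alpha-diversity indices, base the conclusion on the baseline-adjusted between-arm difference with its 95% CI. Label this analysis as added after trial completion, and keep the paired tests as descriptive.
3. If short-chain fatty acids were measured, report the three acids with the same between-arm analysis. If not, leave Hypothesis 1 as written, state that this part was planned but not tested, and draw no conclusion on it.

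The cost is a small amount of modelling on existing data, with no new samples for the microbiota part. Intervals for the sequencing indices will be wide, at about ±0.89 residual SD, and that imprecision should be shown. For the fatty acids the cost is either an analysis of existing values or one explanatory statement.
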